9. STUDY ENROLLMENT AND COMPLETION AT ED VISIT

When the randomized patient has an ED visit for VOE, this patient is enrolled in the study population. The provider (un-blinded) in the ED will access the patient’s randomized analgesic protocol from the EMR for treatment. The patient will only be told what drugs and doses they will receive, but will not be told which analgesic protocol (weight-based or patient-specific) to which they have been randomized, thus the patient is blinded to the randomized arm. Research assistants (RAs), who are also blinded to study arm, will

interview the patient during an ED visit to obtain pain score data for the primary outcome. Only one ED visit per patient is recorded for the primary and secondary outcomes. The study is complete as soon as one post-randomization ED visit is recorded. The patient's randomized analgesic protocol will be removed from the EMR after the study ED visit is recorded. In the event where the ED visit is missed due to no availability of a RA (e.g., in the middle of the night), the next ED visit will be recorded. The RA will periodically review the EMR to obtain information on the missed ED visits for tracking purposes. During the ED visit, the maximum amount of time for study participation is six hours, which begins at placement in an ED treatment area. A brief interview will be conducted every 30 minutes until 1) discharge home, 2) admission to the hospital or assigned to observation status for continued pain management, or 3) after six hours of treatment (maximum data collection period), whichever comes first. Each patient will be allowed to contribute only one ED visit to the study data.

10. FOLLOW-UP DATA COLLECTION.

After the completion of the patient's recorded ED visit, the RA will periodically review the EMR to obtain the number of ED visits and number of hospitalizations within 7 days of the recorded ED visit for collection of secondary outcomes.

11. OUTCOME DETERMINATIONS

1.1 Primary Endpoint

The primary endpoint of the study population is the change in pain scores from the time of placement in a treatment area to the time of disposition (hospital admission, discharged home, assigned to observation status) or a maximum treatment duration of 6 hours, whichever comes first.

1.2 Secondary Endpoints

The secondary outcomes of the study population include the following:

- ED length of stay
- Hospitalization for pain control
- Return ED visits, hospitalizations, or day hospital visits within seven days of the index ED visit

12. PARTICIPANT SAFETY AND ADVERSE EVENTS

12.1 Institutional Review Boards

All sites will submit the study protocol, informed consent form, and other relevant study documents to the Central Institutional Review Board (IRB) for approval.

12.2 Informed Consent

A signed ICF is a requirement for patient inclusion in the study. All patients will have the

purpose of the study, the study interventions and evaluations, and the potential risks and benefits of participation explained to them and their questions answered. If patients consent to participation in this study, they will review and sign the ICF. Study staff at the enrolling site will administer the ICF during hospitalization, a clinic or at the end of an ED visit (for enrollment in future ED visits). At the time of ICF discussion, patients will receive study informational materials and the contact information for the site study staff at the enrolling site.

12.3 Voluntary Withdrawal from the Study

Patients may withdraw at any time during the study without giving reasons and will not suffer disadvantage as a result. In cases of study withdrawal, patient care will continue per the discretion of healthcare providers. Investigators may withdraw patients from the study at any time if upon review the patient meets exclusion criteria.

12.4 Summary of the Risks and Benefits

We do not anticipate that participation in this study will be associated with increased risk beyond that of standard care. Potential side effects for the medications used in the study, such as morphine and hydromorphone, include drowsiness and sedation, nausea, vomiting, light-headedness, and itching. Less common side effects include respiratory depression and lower blood pressure. Both morphine and hydromorphone are currently used in routine clinical practice. The benefit of participation in the study is the generation of an evidence-based treatment analgesic protocol for SCD patients with an ED visit for VOE.

12.5 Collection and Reporting of Adverse Events

An Adverse Event (AE) is any untoward medical occurrence associated with the use of a drug in humans, whether or not it is considered drug related. Only protocol- specific expected AEs occurring during the enrollment ED visit will be collected and reported on the AE eCRF.

12.5.1 Protocol-Specific AEs

The following events are considered expected AEs for this protocol and are reported on the AE eCRF.

- Nausea
- Vomiting
- Pruritis
- SPO₂ < 95 % requiring supplemental use of oxygen via nasal cannula due to opioid therapy
- Moderate or severe sedation
- Drowsiness
- Respiratory depression not requiring intubation or naloxone
- Low blood pressure

AEs are summarized and reported to DSMB in bi-annual meetings.

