6.2. Blinding

The provider will be un-blinded to the analgesic protocol at the time of the patient visit to the ED.

Patients will be told what drug and dose they are receiving during their study ED visit. However, they will remain blinded to the analgesic protocol to which they are randomized. The research assistant performing the study assessments will also remain blinded to the randomized analgesic treatment protocol until all assessments have been completed.

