2.3. Blinding

The patient hematologist will be un-blinded to the analgesic protocol and will write the treatment plan based on the randomized assigned analgesic protocol to be uploaded in uploaded to the electronic medical record (EMR). However, the emergency physician will be blinded to the analgesic protocol at the time of the patient visit to the ED.

Patients will be told what drug and dose they are receiving during their study ED visit. However, they will remain blinded to the analgesic protocol to which they are randomized. The research assistant performing the study assessments will also remain blinded to the randomized analgesic treatment protocol until all assessments have been completed. (section 6)

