3.2. Study Procedures / Blinding

When the randomized patient has an ED visit for VOE, this patient is enrolled in the

study population. The provider (un-blinded) in the ED will access the patient's randomized analgesic protocol from the EMR for treatment. The patient will only be told what drugs and doses they will receive, but will not be told which analgesic protocol (weight-based or patient-specific) to which they have been randomized, thus the patient is blinded to the randomized arm. Research assistants (RAs), who are also blinded to study arm, will interview the patient during an ED visit to obtain pain score data for the primary outcome. Only one ED visit per patient is recorded for the primary and secondary outcomes. The study is complete as soon as one post-randomization ED visit is recorded and 7-day post ED data are extracted from medical records. The patient's randomized analgesic protocol will be removed from the EMR after the study ED visit is recorded. In the event where the ED visit is missed due to no availability of a RA (e.g., in the middle of the night), the next ED visit will be recorded. The RA will periodically review the EMR to obtain information on the missed ED visits for tracking purposes. During the ED visit, the maximum amount of time for study participation is six hours, which begins at placement in an ED treatment area. A brief interview will be conducted every 30 minutes until 1) discharge home, 2) admission to the hospital or assigned to observation status for continued pain management, or 3) after six hours of treatment (maximum data collection period), whichever comes first. Each patient will be allowed to contribute only one ED visit to the study data. (section 9 of the protocol)

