7.6. Safety Outcomes

This section contains bar chart displays of protocol-specific expected adverse event (AE) data, such as nausea, vomiting, puritis, SPO₂ < 95% requiring supplemental oxygen via nasal cannula due to opioid therapy, moderate to severe sedation, drowsiness, respiratory depression not requiring intubation, and low blood pressure.

This section also contains bar chart displays of the incidence of protocol-specific serious adverse events (SAE), including respiratory depression requiring naloxone administration given within the 2 hours of last administration of pain protocol drug, any event resulting in death, any event that is considered a life-threatening complication, any event requiring admission to the intensive care unit (ICU), any event requiring intubation, and hospitalizations with the primary reasons.

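### The desaturation AE counts only cannula-treated events attributed to opioids, with no named assessor or criteria, yet this row is tested between arms that differ in opioid dose

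*Protocol*

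**What the plan says.** Protocol 12.5 gives a general definition under which an occurrence is an AE "whether or not it is considered drug related". It then restricts collection to a list: only protocol-"specific expected AEs occurring during the enrollment ED visit will be collected and reported on the AE eCRF".

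Protocol 12.5.1 lists eight items. Seven are described without reference to cause. The eighth, SpO2 below 95%, must also be "requiring supplemental use of oxygen via nasal cannula due to opioid therapy". SAP 7.6 keeps both conditions ("requiring supplemental oxygen via nasal cannula due to opioid therapy"), as does the row label in SAP Table 14.1. That table compares the arms with a p-value, following SAP 4.3 and Protocol 13.10, which call these exploratory safety outcomes.

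Causality guidance appears only for SAEs (Protocol 12.6.1), where the investigator makes the assessment. There is none for AEs.

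The documents disagree on blinding of the ED clinician. Protocol 6.2 states "The provider will be un-blinded to the analgesic protocol at the time of the patient visit to the ED". Protocol 9 and SAP 3.2 agree with it (SAP: "The provider (un-blinded) in the ED"), as does the SAP synopsis. SAP 2.3 states that "the emergency physician will be blinded to the analgesic protocol at the time of the patient visit to the ED". The research assistant is blinded throughout.

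**The concern.** An AE row compared between randomized arms should be defined so that the same event counts in the same way in both. Here an event enters the row only after someone decides that the opioid caused it. Opioid dose is what separates the arms: Protocol 4 names the starting dose as the primary difference, and Protocol Table 2 also gives different repeat-dose provisions. Knowledge of the dose given could therefore influence the attribution. If the attributed share differs by arm, the row can show a difference where none exists or conceal one that does. No rule is stated that would keep the judgement uniform.

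The device condition is a separate matter. A patient whose desaturation is managed with something other than a nasal cannula does not meet this item, and only listed AEs are collected.

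**Working it through.** **1. No plan figure to reproduce.** The documents give no desaturation rate, attributed share or power for this row. The first check is therefore textual.

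| Question | What the documents give |
|---|---|
| Is attribution required of other listed AEs? | No; one item of eight (Protocol 12.5.1) |
| Who attributes? | Not stated; SAE causality only (Protocol 12.6.1) |
| By what criteria? | None for AEs |
| Does the ED provider know the arm? | Yes in Protocol 6.2 and 9, SAP synopsis and 3.2; no in SAP 2.3 |
| Is the row tested between arms? | Yes (SAP 4.3, Table 14.1) |

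**2. What the cannula condition leaves out.** Other lines catch much of the more serious end. Respiratory depression is its own AE, with no cause or device condition. Respiratory depression needing naloxone, ICU admission, intubation, life-threatening events and death are SAEs (Protocol 12.6.1). What remains is desaturation treated with a non-cannula device that is not also recorded as respiratory depression (a term the documents do not define) and meets no SAE line.

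**3. Whether the 30-minute SpO2 data fill the gap.** SpO2 is recorded every 30 minutes whatever the cause (Protocol Table 2) and summarised by arm over time (SAP 7.4, 10.4, 16.1). Those summaries are distributions at each time point. No count of patients below 95% is planned. Readings after oxygen starts can look normal, and neither the assessment schedule nor SAP 16.1 lists oxygen use.

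**4. Illustration of size; all rates are assumed.** Take n = 230/2 = 115 per arm, true rate p, attributed shares a1 and a2, and two-sided 0.05. The observed rates are p1 = p·a1 and p2 = p·a2. The chance of a nominally significant result is approximately

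Φ[(|p1 − p2| − 1.96·SE0)/SE1], with SE0 = √[2·p̄(1 − p̄)/n], p̄ = (p1 + p2)/2 and SE1 = √{[p1(1 − p1) + p2(1 − p2)]/n}.

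Example: p = 20%, a = 90% against 70%. Then p1 = 0.18, p2 = 0.14, p̄ = 0.16, SE0 = √(0.2688/115) = 0.0483 and SE1 = √(0.2680/115) = 0.0483. The argument is (0.04 − 0.0948)/0.0483 = −1.13, so the probability is about 13%.

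Chance of a false nominal difference when the true rates are equal:

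| True rate, both arms | 90% vs 70% attributed | 90% vs 50% attributed |
|---|---|---|
| 5% | 6% | 13% |
| 10% | 8% | 22% |
| 20% | 13% | 42% |
| 30% | 19% | 61% |

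The other direction: a true 20% against 10% has about 57% power with full capture. If 70% of events are attributed in the higher-rate arm and 90% in the other, the observed rates are 14% and 9% and power is about 22%. At 50% against 90% the observed rates are 10% and 9%, and power is about 4%, no better than the test's own size.

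In counts: 115 × 0.20 = 23 true events per arm. Attributing 80% and 50% gives 18.4 and 11.5, or about 18 against 12 patients, a ratio of 18.4/11.5 = 1.6 from attribution alone. The uncorrected chi-square on 18/115 against 12/115 has pooled rate 30/230 = 0.130, SE 0.0444 and z = 0.0522/0.0444 = 1.17, so p is about 0.24.

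With equal shares, the ratio of the two rates is preserved. Events are still dropped, and the absolute difference shrinks.

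**The case against.** A restricted AE list with its own item definitions is a legitimate design choice. Separating opioid-related from disease-related desaturation is a sensible aim where acute chest syndrome is a known complication with its own adjudication (Protocol 12.8). The AE eCRF and the manual of operations are not among the documents and may name the assessor. The outcome is exploratory and is to be read with clinical judgement. The assumed 18 against 12 would not reach nominal significance. The 30-minute SpO2 data would give a reader some check on the row.

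Most of this stands, and it limits the weight of the point. It does not supply a rule for attribution in the protocol or SAP, and the aim of isolating opioid-related events can be met with a sub-row.

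Two stronger readings are tempting and go too far. A reader might infer that un-blinded ED clinicians make the attribution and that the row is therefore biased. Protocol 9 does say "The provider (un-blinded) in the ED will access the patient’s randomized analgesic protocol from the EMR for treatment", but no section says that this provider decides cause, and SAP 2.3 contradicts the un-blinding. A reader might also infer that patients needing more respiratory support go uncounted. The separate respiratory depression AE and the SAE lines rule that out as a general statement; only the gap in step 2 of the working remains.

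**Conclusion.** The point holds as a minor defect of definition. The inconsistency between Protocol 12.5 and 12.5.1, the lack of an assessor or criteria, and the between-arm test can all be read directly from the text. That attribution might differ by arm is a reasoned possibility resting on the dose contrast; the documents do not show that it would, or in which direction. Every figure in the illustration depends on assumed rates: across the scenarios shown, the false-difference probability runs from about 6% to about 61%, and with equal attribution there is no excess. How often the device gap would arise is also unknown. The primary endpoint, sample size, type I error and futility rule are unaffected.

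**What to change.** In Protocol 12.5.1, SAP 7.6 and SAP Table 14.1:

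- Define the item as SpO2 below 95% with new or increased supplemental oxygen, by any device, after the first protocol dose and regardless of cause.
- Use that row for the comparison between arms.
- Keep judged due to opioid as a yes/no field shown as a sub-row, and state who completes it and on what criteria.
- Reconcile SAP 2.3 with SAP 3.2 and with Protocol 6.2 and 9 on whether the ED provider knows the assigned protocol.

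If the eCRF cannot change, add to the SAP a per-arm count of patients with any SpO2 below 95% after the first protocol dose, taken from the existing 30-minute readings. This is weaker because it carries no information on oxygen use.

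The cost is a wording change and one yes/no field. It alters what is counted and leaves patient care alone. Some disease-related desaturation will be included, so the reported rate will rise somewhat in both arms; randomization should balance that part on average. The opioid-attributed count stays available in the sub-row.

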12.6 Collection and Reporting of Serious Adverse Events

An adverse event is considered a serious adverse event (SAE) if, in the view of the investigator or sponsor, results in any of the following: death, is life threatening, requires inpatient hospitalization or prolongation of existing hospitalization,* is a persistent or significant incapacity or substantial disruption of the ability to conduct normal life functions, a congenital anomaly/birth defect, or an important medical event. Only protocol-specific SAEs will be collected and reported on the SAE eCRF. Specific timing on collection and reporting of SAEs is specified below.

*For this protocol, if the study ED visit resulted in a hospitalization for pain control, this hospitalization will be considered the *index* hospitalization and will not be considered an SAE. Hospitalizations for VOE treatment within 7 days post the ED visits will also not be considered SAEs.

12.6.1 Protocol-Specific SAEs

SAEs are collected from the time of first administration of pain protocol drug during the study ED visit through 7 days post ED visit and reported on the SAE eCRF. The following SAEs are to be considered.

- Respiratory depression requiring naloxone administration given within 2 hours of last administration of pain protocol drug.
- Events resulting in death
- Events that are considered life-threatening complications
- Events requiring admission to Intensive Care Unit (ICU) or intubation within 7 days of first administration of pain protocol drug during the enrollment ED visit.

SAEs occurring during the protocol administration or within 7 days post enrollment ED visit, along with the investigator's assessment of relatedness, will be recorded by the site on the SAE eCRF in the EDC within 24 hours of knowledge of the event. The Data Coordinating Center (DCC) will receive an EDC email notification of SAE data once entry by the site. The DCC will notify the NHLBI within two business days of receipt of the email notification. Once notified, the NHLBI will notify the DSMB.

If patients experience any SAEs during the ED visit, the treatment protocol will be discontinued. Subsequent VOE treatment will be determined by the ED provider.

Assessment of Serious Adverse Event Causal Relationship

The investigator must assess the relationship of any SAE to the use of the drug, based on available information, using the following guidelines:

Not Related: There is not a reasonable causal relationship to the product and the adverse event.

Related: There is evidence to suggest a causal relationship, and the influence of other factors is unlikely.

Assessment of Serious Adverse Event Intensity

The determination of serious adverse event intensity rests on medical judgment of a medically qualified investigator. The severity of SAEs will be graded using the following definitions:

- **Mild:** awareness of sign, symptom, or event, but easily tolerated;
- **Moderate:** discomfort enough to cause interference with usual activity and may warrant intervention;
- **Severe:** incapacitating with inability to do usual activities or significantly affects clinical status, and warrants intervention.

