8.3 Odd Volume Doses for both analgesic protocols: One barrier to analgesic protocol implementation was the odd doses that resulted in the need to administer a volume of drug less than the amount in which it was supplied. This required “wasting” by the ED nurses and verification by a second nurse. We have consulted with a multidisciplinary team consisting of a pain expert, adult hematologist, and an emergency department physician to determine a strategy to select a final dose that will minimize the need for odd doses and wasting procedures (e.g. morphine 4.3 mg, or hydromorphone 1.3 mg). All doses of morphine can be ordered in increments of 2 mg and doses of hydromorphone can be ordered in increments of 0.5 mg. These doses remain consistent with the patient-specific and weight-based doses with rounding to a safe dose, and will significantly reduce the need to waste drug in most cases. We used this information when creating Table 1. Table 2 describes differences between analgesic protocols in agent, dose, route, monitoring, repeat doses and hydration. The primary difference between analgesic protocols is dose and the provision to increase weight-based doses if insufficient pain relief.

Table 2: Comparison of NHLBI Recommendations: Patient specific vs. Weight-based analgesic Protocol

	Patient-specific analgesic protocol	Weight-based SCD analgesic protocol
Agent	To be determined (TBD) by SCD provider after randomization for use at a future ED visit (morphine sulfate or hydromorphone)	To be determined (TBD) by SCD provider after randomization for use at a future ED visit (morphine sulfate or hydromorphone)
Dose	TBD a priori by SCD provider, based upon current outpatient opioid therapy, if applicable, and past doses required to treat VOE during past ED visits or hospitalizations.	TBD a priori by SCD provider. Initial dose = weight based hydromorphone 0.02 mg/kg morphine sulfate 0.1 mg/kg
Route	Intravenous (IV) unless unable; Sub-cutaneous when IV access is difficult.	Intravenous (IV) unless unable; Sub-cutaneous when IV access is difficult.
Monitoring	Per routine standard of care Q 30 minutes per research protocol / research assistant (sedation level, SpO ₂ , BP, HR, RR).	Per routine standard of care Q 30 minutes per research protocol / research assistant (sedation level, SpO ₂ , BP, HR, RR).

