Repeat doses	TBD by SCD provider – Q 20-30 minutes as required to treat unrelieved pain. No maximum dose set.	Q 20-30 minutes for unrelieved pain. All additional doses, if required, may be provided at the same dose as the 1 st dose, or no more than a one time 25% increase above the original dose.
Intravenous hydration	Maintenance rate (unless dehydrated) when patients are unable to drink fluids adequately.	Maintenance rate (unless dehydrated) when patients are unable to drink fluids adequately.

Once the patient’s analgesic protocol has been developed (patient-specific or weight-based) by the hematologist/sickle cell team, the research team will be notified. The research team will ensure the analgesic protocol is uploaded to the electronic medical record (EMR) within one week of receipt. The analgesic protocol will be available in the EMR for future ED visits.

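### In the study ED visit, respiratory depression reversed with naloxone more than 2 hours after the last protocol dose fits neither of the protocol's two respiratory-depression items, unless it is fatal, intubated, sent to ICU or judged life-threatening

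*Protocol*

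**What the plan says.** **Protocol, AEs.** Section 12.5 limits collection to the protocol's own list: "expected AEs occurring during the enrollment ED visit will be collected and reported on the AE eCRF". The respiratory-depression item on that list (Section 12.5.1) is "Respiratory depression not requiring intubation or naloxone".

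**Protocol, SAEs.** Section 12.6 gives a general definition of seriousness and then narrows collection: "Only protocol-specific SAEs will be collected and reported on the SAE eCRF". Section 12.6.1 has four items: "Respiratory depression requiring naloxone administration given within 2 hours of last administration of pain protocol drug"; death; life-threatening complications; and ICU admission or intubation within 7 days. The same section adds a consequence: "If patients experience any SAEs during the ED visit, the treatment protocol will be discontinued".

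**SAP.** The AE row for respiratory depression, in Section 7.6 and in the table in Section 14.1, is defined by the absence of intubation alone and does not mention naloxone. The SAE row in Section 14.2 keeps the 2-hour limit. Section 7.6 describes its AE rows as protocol-specific. The SAP governs the final report (SAP Section 1).

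**Related provisions.** Sedation level, SpO2, blood pressure, heart rate and respiratory rate are monitored "Q 30 minutes per research protocol / research assistant" (Protocol Table 2). SAP Section 16.1 tabulates them by arm at 30-minute steps up to 360 minutes. The names, doses and times of ED drugs are recorded (Protocol Appendix A).

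**The concern.** The two protocol items look like complements, but they are cut at different places. The AE item drops a case as soon as naloxone is needed, whenever it is given. The SAE item picks the case up only if the naloxone came within 2 hours of the last protocol dose. A later reversal is left between them, and because both lists are closed, no residual category catches it. The order is also the wrong way round: depression that resolved without an antagonist is counted, and depression that needed one may not be.

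Protocol Section 12.4 names respiratory depression as a risk of the study drugs, and the protocol describes dose as the main difference between the arms. Counts of this event by arm are therefore a natural part of the safety comparison. During the trial, a late-reversed case could reach the monthly Steering Committee review of side effects, or the twice-yearly AE summary to the DSMB, only through its signs. At the end, the SAP's different row label leaves a reader unsure which definition the AE table uses.

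**Working it through.** The plan states no figure on this point. The check is an enumeration, followed by a test of whether the gap can occur.

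**Step 1. Restrict to the cases in question.** Take respiratory depression during the enrollment ED visit and set aside death, intubation, ICU admission and events judged life-threatening, since Section 12.6.1 takes those as SAEs. Three cases remain.

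| Case | Protocol AE item (12.5.1) | Protocol naloxone SAE item (12.6.1) | SAP AE row read literally (7.6, 14.1) | SAP SAE row (14.2) |
|---|---|---|---|---|
| (a) no naloxone | yes | no | yes | no |
| (b) naloxone within 2 h of last protocol dose | no | yes | yes | yes |
| (c) naloxone later than 2 h | no | no | yes | no |

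**Step 2. Count under the protocol.** AE: 1 (a). SAE: 1 (b). Unclassified: 3 − 1 − 1 = 1 (c).

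**Step 3. Count under the SAP label, read literally.** The AE row takes 3 of 3, against 1 of 3 under the protocol item, and case (b) fits both the AE and the SAE row. This reading applies only if the AE form or the table programming uses the SAP's words. If the form uses the protocol's words, case (c) is never entered under this item and the SAP row cannot recover it.

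**Step 4. Can case (c) occur?** It needs more than 120 minutes without a protocol dose. Repeat doses in the patient-specific arm are "Q 20-30 minutes as required to treat unrelieved pain. No maximum dose set", and the weight-based arm has the same interval. The gap is thus at least 120/30 = 4 redosing intervals at 30 minutes, or 120/20 = 6 at 20 minutes. In Section 9, "the maximum amount of time for study participation is six hours, which begins at placement in an ED treatment area". For reversal inside that period the last dose must come before 360 − 120 = 240 minutes from placement. Participation can end sooner, at disposition. The pilot's mean ED stay was 278 minutes from arrival (Protocol Table 3); in a stay of that length the last dose must come before 278 − 120 = 158 minutes from arrival. The case is possible, but the window is narrow.

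**Step 5. Count after rewording the AE item** as any respiratory depression that meets no protocol-specific SAE criterion. AE: 2 (a and c). SAE: 1 (b). Unclassified: 3 − 2 − 1 = 0. In both: 0. The cases set aside in Step 1 remain SAEs.

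**The case against.** **Other items may catch the event.** This stands in part. An investigator may judge a reversed case life-threatening, or the patient may go to ICU, and either makes it an SAE. A reader might infer that late-reversed cases fit no protocol item whatever. The documents do not support that; the gap is confined to the two respiratory-depression items and to cases that meet none of the other SAE criteria.

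**The signs are captured anyway.** This also stands. Sedation, drowsiness and low SpO2 needing oxygen are AE items, and SAP Section 16.1 shows respiration rate, SpO2 and sedation score by arm regardless of how an event is classified. These do not record that respiratory depression occurred and needed reversal.

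**The 2-hour limit is a deliberate attribution window.** That could justify leaving late cases off the SAE list. It does not justify leaving them off the AE list, because Section 12.5 defines an AE without regard to drug causation.

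**The SAP row is just a short label.** This may well be right. Section 7.6 calls its rows protocol-specific, and the AE form is not in the documents. A reader might infer that the AE table will double-count early reversals or absorb late ones; that is possible but not shown.

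**The patient-specific arm has no dose cap.** A reader might infer that missed cases would gather in that arm. Nothing supports this: case (c) requires more than two hours without a protocol dose, and no provision links the absent cap to late reversal.

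**The reworded item still does not show the reversal.** True. It puts cases (a) and (c) in one row; the naloxone itself would have to be read from the ED drug record, if entered there. The rewording cures the missing classification only.

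**Conclusion.** The gap in the protocol is real and follows from the wording of four adjoining sections. One of the three in-visit cases has no respiratory-depression item, and it is a more serious case than one that is counted. What is lost is the event's classification as respiratory depression in AE reports, not all trace of it.

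The SAP mismatch is a separate and weaker matter. It alters the AE table only if the form or the programming follows the SAP's wording, and it has no bearing on safety reporting during the trial, which follows the protocol lists.

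The number of patients affected cannot be derived, since the documents give no rate of naloxone use. It is probably small, given the dose-free gap required. No difference between arms is shown. The primary endpoint, power and analysis population are unaffected. The conclusion assumes that sites apply the two closed lists as written and that the AE form mirrors the protocol list. It is a point to consider: minor in consequence, and cheap to correct.

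**What to change.** Word the AE as *respiratory depression not meeting a protocol-specific SAE criterion* in Protocol Section 12.5.1, SAP Section 7.6, the AE table in SAP Section 14.1 and the matching AE form label. Every in-visit case then falls in exactly one category.

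The cost is a one-line amendment to the protocol and to the SAP, presumably with central IRB review of the protocol change, and a form label edit if the form uses the same words. Sites will need to check the item against the SAE list in Section 12.6.1. No new data are required, because the timing of naloxone already has to be established for the SAE item. The change adds no SAE and leaves the discontinuation rule as it is.

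Dropping the 2-hour limit from the SAE item is a separate choice for the sponsor and not part of this fix. It would add SAE reports, and it would extend mandatory discontinuation of the treatment protocol to late-reversed cases.
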